To assess preliminary efficacy in terms of within-group improvement.	Efficacy outcomes focusing on general anxiety, depressive symptoms, the fear of cancer recurrence, and quality of life

Methods

[figure not shown]
Design

This is a randomized factorial trial (N=400; 2x2x2 with a cell size of 50; for the pilot study: N=48; 2x2x2 with a cell size of 6) of therapist-guided Internet-delivered psychological treatment for cancer survivors with long-term clinically significant anxiety or depression despite a good prognosis. Study site is Karolinska Institutet, Stockholm, Sweden. The sample size allows for two-sided conventional mean tests of small ($d \approx 0.3$) component effects (n=200 vs. 200) with 80% power of, given an alpha of 5% and up to 14% missing data post-treatment. The pilot study will have a feasibility focus, though the sample size will also be sufficient to study average within-group effects with 80% power in two-sided tests of moderate effects ($d \approx 0.45$) on efficacy outcomes measured at two time points, given a 5% alpha and up to 20% missing data post-treatment. The study protocol will be reviewed by the Swedish Ethical Review Authority and preregistered at ClinicalTrials.gov. All procedures will adhere to the declaration of Helsinki and the relevant privacy and data management legislation.

Eligibility criteria

- a) Cancer survivor 0.5-20 years after main therapy. For the pilot study: survivor of breast cancer (n=24), testicular cancer (n=12), or thyroid cancer (n=12),
- b) Clinically significant anxiety or depression (PHQ-9 ≥ 10 , or GAD-7 ≥ 8) (24, 25)
- c) At least 18 years old
- d) Resident of Sweden (listed and de facto). For the full trial: Stockholms län, Västra Götalands län, or Skåne län.
- e) Sufficient technical knowledge and knowledge of the Swedish language to take part in a text-based online treatment
- f) Continuous access to an electronic device that can be used to access the study web platform
- g) Not recurrent thoughts of suicide, as based on clinical judgement aided by the structured interview (see below) and the MADRS-S item 9
- h) No severe medical condition (e.g., very poor prognosis, stage IV cancer), severe psychiatric disorder (e.g., psychotic disorder, bipolar disorder, or severely debilitating substance use disorder, severe depression), or medical treatment (e.g., chemotherapy, immunotherapy, radiotherapy) that makes the treatment unfeasible
- i) No other ongoing psychological treatment

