The following randomization procedure will be piloted: Each cohort size is a multiplier of the number of unique combinations of treatment components (i.e., 8). After completion of the pre-treatment assessment, and separately for each cohort, randomization is achieved using a true random number service (www.random.org), managed by an individual otherwise not involved in the trial. Tentatively, based on the outcome of the 2023 pilot trial and feasibility outcomes, interventions will be built using the following components derived from existing protocols: (a) behavioral activation with existential themes and emphasis on values (44, 45) and relationships, (b) systematic exposure with mindfulness training with a focus on anxiety about health and/or death (46), body image, and cancer-related trauma, and (c) an overview of self-management techniques in terms of physical exercise, dietary advice, and strategies for improved sleep. Fifty patients are randomized to each combination of treatment components: a, b, c, a+b, a+c, b+c, a+b+c, and also a null group where support and rudimentary clinical information is given to control for the effect of attention from a clinician and enrollment in the structured online format, resulting in the total sample size of 400. The point of administering all these combinations is to make it possible to model the simple effect (added contribution) of each component to the treatment effect, and also all component interactions. After the follow-up phase (see below), for ethical reasons, controls are crossed over to the a+b+c combination though without therapist support. To the extent that this is found feasible in the pilot study, the treatment content for all combinations of components will be developed with similar readability (47), interactivity, and picture content. Importantly, even in the null group attention control, the treatment will involve support from a clinician, information about the negative long-term effects of cancer and will offer participants the possibility of observing their own symptoms in a systematic manner.

Partial blinding of study design

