In order for the analysis of treatment components to be valid and helpful in the design of future therapies, it is important that the participants remain blinded to the randomized factorial design throughout the full measurement period. (Full blinding, i.e., where the patient and therapist remain unaware of the treatment condition, is not possible in psychological treatment research (48).) Regardless of condition, participants will be informed that they take

part in an Internet-delivered support program for improved mood in the aftermath of cancer. At the 12-months follow-up (3 months in the pilot study), a written blinding check will then be conducted whereby participants are asked about whether they are aware of which treatment variants that are being compared and why. Participants will then be unblinded (debriefed) and those in the attention control (see above) will be offered the full material from the full factor version of the treatment.

Secondary outcome: registry data on healthcare consumption

If funding is secured for this secondary outcome, registry data on health care consumption will also be collected, pertaining to the 2 years immediately before treatment, and the 2 years immediately following treatment. To ensure access to health consumption data, patients will be recruited exclusively from Stockholms län, Västra Götalands län, and Skåne län for the full trial. This will not be implemented in the pilot study.

Data safety and management

Throughout the project, data management plans and documentation will be maintained and revised in accordance with up-to-date guidelines of Karolinska Institutet. The study web platform will employ encrypted traffic and two-factor authentication. Researchers in the project have access to study data, which is stored and managed in accordance with European Union and Swedish data protection and privacy legislation, and the guidelines of Karolinska Institutet. Personal data are exclusively stored in systems classified and provided specifically for this purpose by Karolinska Institutet. Study results are reported in a manner that does not make it possible to identify individual participants.

Statistical analysis

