The main pre-post efficacy outcomes will be analysed by an individual blinded to treatment identity (each component is coded simply as -0.5 vs. 0.5 without labels in the dataset). Hierarchical multiple imputation by chained equations will be employed to manage missing data, and imputation will be conducted separately for each cell so as to maintain interaction effects (49). Efficacy outcomes are analysed using fully factorial linear mixed models, so that the simple effects of the components, and also their interactions, can be quantified and tested. Health economic analyses will focus on comparing the most potent treatment configuration (cells are collapsed if no component shows superiority) to the null group (i.e., rudimentary information and support from a clinician only). Mediation analysis will be conducted within a structural equation modelling framework, based on parallel process growth models. The pilot study will not focus on inferential statistics, but rather the feasibility outcomes (see Table 1).

Ethical considerations

This randomized factorial trial and the pilot study are conducted in accordance with the declaration of Helsinki, current Swedish and European Union privacy and data management legislation, and internal guidelines of Karolinska Institutet. The project will be preregistered online, and results including the treatment content will be published open access so as to ensure transparency and that findings benefit the research field. Applicants will be required to provide informed consent in order to be included as participants.

Psychological treatments can induce unwanted effects for example in terms of deterioration or an increase in symptoms, disappointment with the quality of treatment, dependency on the therapist, stigma associated with enrollment, hopelessness as a consequence of insufficient efficacy, or a sense of failure or reduced self-efficacy (50). Based on the existing evidence base, the negative effects of therapist-guided Internet-delivered psychological treatments

similar to that evaluated here are typically limited (51, 52). In contrast, the beneficial effects for example on anxiety are more likely to be at least moderately sized on average. Adverse events and participants mood is tightly monitored throughout the intervention. Heightened suicidal ideation is automatically flagged and cause for clinical assessment. Participants are referred to routine services if necessary.

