Preparatory work in terms of writing protocols, producing content, and submitting the work for ethical review will take place in May-September 2023. We plan to involve patient representatives in the treatment drafting process. Hands-on procedures are first evaluated, and recruitment is initiated, in September 2023. Recruitment for the pilot trial is complete around the end of 2023. The finalization of all routines for the full-scale trial, including the recruitment of additional psychologists interested in contributing to the project by serving as therapists in exchange for co-authorship, will be completed during the January-June period. Recruitment of participants for the full-scale randomized factorial trial will begin in August 2024. From then on, approximately 80 participants will be recruited each semester until the end of 2026. We expect the last 12-month follow-up assessment to be completed in December 2027. Manuscripts will be submitted for publication throughout 2028 to 2030.

Significance

This project can lead to substantial societal gains. The population of cancer survivors who experience long-term distress is substantial, and access to structured treatment is insufficient. Internet-delivered psychological treatment is relatively easy to scale up and disseminate, for example in the primary care context, and the development of a free-to-use treatment protocol based on rigorous evaluation in clinical trials could potentially have pervasive effects on suffering and health care utilization. Though the project will proceed in accordance with this research plan, the outcome of the pilot study can also inform the precise design of the full-sized clinical trial and sufficient amendments will be submitted for ethical review as deemed necessary. Experiences from the randomized factorial trial can inform clinical practice in that we will arrive at an evidence-based Internet-delivered psychological treatment for cancer survivors with clinically significant psychiatric symptoms.

References

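### The plan gives no rule for matching unblinded therapists to participants and names neither cohort nor therapist in the efficacy model, so component effects are not protected against uneven therapist caseloads

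*Combined protocol and SAP*

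**What the plan says.** The section on randomized allocation of treatment components sets the balancing unit: "Each cohort size is a multiplier of the number of unique combinations of treatment components (i.e., 8"). The list is then produced cohort by cohort: "After completion of the pre-treatment assessment, and separately for each cohort, randomization is achieved using a true random number service". A person with no other part in the trial runs this step. No balancing factor other than cohort is named.

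Every participant has a therapist, who answers messages individually, and homework is adapted to the patient (General format of Internet-delivered treatment). Therapists know the condition: "Full blinding, i.e., where the patient and therapist remain unaware of the treatment condition, is not possible" (Partial blinding of study design). The timetable paragraph just before the Significance section plans the "recruitment of additional psychologists interested in contributing to the project by serving as therapists in exchange for co-authorship". No passage states how many therapists there will be, how or when a participant is matched to one, or whether each therapist covers all eight combinations.

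On analysis, the plan says: "Efficacy outcomes are analysed using fully factorial linear mixed models", with the components and their interactions as the effects to be estimated. Random effects are not listed, and neither cohort nor therapist is mentioned.

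**The concern.** The aim is the separate contribution of each component, so the estimand is a contrast between the 200 participants who receive a component and the 200 who do not. Randomisation makes the participants comparable across that contrast. It does the same for the therapists only if matching is independent of condition or balanced over it, and the plan commits to neither.

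If caseloads leaned toward one level of a component, differences between therapists would enter that component's estimate, and a model without a therapist term would understate its variance. The null group has a related exposure. It is there to hold clinician attention constant, which depends on its clinicians being comparable with those in the active cells.

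Cohort is a lesser matter. The trial randomises by cohort, so the analysis would normally carry it, but leaving it out costs only precision.

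**Working it through.** **1. The plan's own figure.** The Design section states "This is a randomized factorial trial (N=400; 2x2x2 with a cell size of 50"), sized for "two-sided conventional mean tests of small ($d \approx 0.3$) component effects (n=200 vs. 200") with 80% power, "given an alpha of 5% and up to 14% missing data post-treatment". For d = 0.3, 80% power and two-sided 5% alpha, the normal approximation gives 2 × (1.960 + 0.842)² / 0.3² = 174.4, so 175 per level. Allowing for 14% missing, 175 / 0.86 gives 204 per level, or 408 in total. Multiplying instead, 175 × 1.14 gives 200 per level, or 400. With 200 × 0.86 = 172 observed per level, power is 79.4%. The stated size reproduces, with no allowance for clustering by therapist.

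**2. Effect of uneven caseloads.** Inputs from the documents: 400 participants, 200 per level. Assumed: T = 10 or 20 therapists with equal caseloads m = 400/T, and a therapist ICC of 0.01 or 0.05. A share s of each caseload sits on one level, with half the therapists leaning each way. Therapist effects are taken as unrelated to the direction of the lean. Outcome variance is set to 1 and missing data are ignored.

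- Therapist part of the contrast variance: T × (m(2s − 1)/200)² × ICC
- Residual part: 4(1 − ICC)/400
- Variance used by a model without therapist: 4/400 = 0.0100
- True type I error: 2 × P(Z > 1.96 / √(true variance / 0.0100))

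Worked case, T = 10, ICC 0.05, s = 0.80: therapist part 10 × (40 × 0.6/200)² × 0.05 = 0.0072; residual part 0.0095; total 0.0167. The variance ratio is 1.67, 1.96/√1.67 = 1.517, and type I error is 12.9%.

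| Caseload split | T = 10, ICC 0.01 | T = 10, ICC 0.05 | T = 20, ICC 0.05 |
|---|---|---|---|
| 65/35 | 5.3% | 6.5% | 5.5% |
| 80/20 | 6.6% | 12.9% | 8.7% |
| 100/0 | 9.6% | 25.4% | 16% |

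Repeating this with 172 per level, 8 to 20 therapists and the same ICC range gives 4.8% to 5.4% at 60/40, 5.4% to 10.8% at 75/25, and 6.9% to 26.6% under full specialisation. Power at 75/25, computed with the true variance, runs from 78% down to 63%.

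**3. Therapists assigned independently of condition.** A simulation of 20,000 trials with 10 therapists, ICC 0.05 and 172 per level, with therapist drawn at random for each participant and left out of the test, gives a type I error of 4.9%.

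**4. What a therapist term can recover.** If every therapist treats both levels, the within-therapist contrast keeps a fraction 4s(1 − s) of the information: 4 × 0.65 × 0.35 = 91% at 65/35 and 4 × 0.8 × 0.2 = 64% at 80/20. At s = 1 it keeps none.

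**5. Omitting cohort.** Five cohorts of 80 are assumed; 80 is the stated recruitment per semester, not a stated cohort size. With cells balanced within cohort and cohort ignored, simulated type I error is 4.9%, 4.6% and 4.1% at cohort ICC 0.01, 0.05 and 0.10. The test is slightly conservative.

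**6. After the fix.** With balanced caseloads and therapist in the model, the contrast variance at 172 per level is (1 − ICC) × 2/172. Power is 79.8%, 80.2% and 81.4% at ICC 0.01, 0.02 and 0.05.

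**The case against.** The strongest reply is that nothing in the documents suggests skewed caseloads. A reader might infer that therapists are assigned after the allocation is known, that they choose the variants they know best, or that they differ in experience. The text supports none of these. It is silent on timing and on who decides, and it says only that more psychologists will be recruited. Random assignment is a plausible default and gives no inflation. This stands: the larger error rates describe a practice that no passage describes.

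A reader might also infer that the model excludes therapist and cohort. It does not go that far. The random effects are simply not listed, and since the outcome is modelled over weekly measurements the model must contain more than component terms. Nor is it right that therapist and component could never be separated afterwards, because under partial imbalance a therapist term separates them with some loss of precision.

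There are mitigating features too. Most content is standardised text, and the principal investigator supervises therapists continuously, both of which may keep the ICC low. Working alliance is measured in week 2. The randomisation procedure is itself being piloted, the pilot does not focus on inference, and amendments before the full trial are foreseen.

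These points make the risk conditional and place it mainly in the full trial. They do not supply the missing matching rule or model terms.

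**Conclusion.** The point holds as a gap in specification with a conditional consequence. Balance is secured over the eight cells within cohort and nowhere else, therapist matching is unstated, and the efficacy model names neither factor. Confounding of component with therapist is possible, not shown.

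The sizes rest on assumed therapist numbers, ICCs and caseload splits. At modest imbalance the inflation is small; it becomes serious only with strong skew, and only full specialisation is beyond repair at analysis. If skill were related to the direction of the lean, the result would be bias in the estimate as well as understated variance, which these figures do not measure. Omitting cohort does not threaten validity and costs a little precision. The change is worth making before the full trial because it is inexpensive and full specialisation could not be undone later.

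**What to change.** **Statistical analysis section.** Add cohort, the unit within which participants are randomised, and therapist to the mixed models as pre-specified terms.

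**Randomized allocation section.** Fix each participant's therapist after the pre-treatment assessment and before the allocation list is drawn. Then randomise within cohort so that each therapist's caseload is approximately balanced over both levels of all three components. Where cohorts are too small for this, assign therapists at random, independently of condition. The independent person who already runs the randomisation can do either. Record the therapist for every participant, and try the procedure in the pilot.

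**Cost.** One extra step before allocation, two model terms, some caseload planning, and less freedom to match therapists to variants. Strict blocks of eight per therapist would need eight participants per therapist in each cohort, which small cohorts may not provide; hence approximate balance or the random alternative. The sample size does not change.

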Participants complete validated self-report questionnaires at screening, before treatment, each week during treatment, after treatment, and 3 months after treatment. These are administered online in Swedish (Table 2). In the pilot study, follow-up will take place 3 months after treatment (not at 6 or 12 months).

Table 2. Validated self-report questionnaires administered in the study

Questionnaire	Outcome	Ref	SN	PRE	WK	PST	6MFU	12MFU
Screening and safety only								
Alcohol Use Disorders Identification Test (AUDIT)	Alcohol use	(27)	x					
Drug Use Disorders Identification Test (DUDIT)	Drug use	(28)	x					
Hospital Anxiety and Depression Scale (HADS)	General distress	(29)	x					
Montgomery-Åsberg Depression Rating Scale item 9	Suicidal ideation ^a	(30)	x	x	x	x		
Symptom domains and similar								
36-Item Short Form Health Survey (SF-36)	Health-related quality of life	(31)		x		x		
7-item general anxiety questionnaire (GAD-7)	General anxiety	(32)	x	x ^b				
9-item Patient Health Questionnaire (PHQ-9)	Depression symptoms	(33)	x	x ^b				
9-item Fear of Cancer Recurrence Inventory (FCRI-9)	Fear of cancer recurrence	(34)		x	x	x	x	x
14-item Health Anxiety Inventory (HAI-14)	Health anxiety	(11)		x		x	x	x
Somatic Symptom Scale 8 (SSS-8)	Somatic symptom burden	(35)		x		x	x	x
Body Image Scale (BIS)	Body image	(36)	x			x		
12-item WHO Disability Assessment Schedule 2.0 (WD2-12)	Disability	(37)	x	x		x	x	x
Process and target variables								
3-item Behavioral Activation for Depression Scale – Activation (BADS-AC-3)	Behavioral activation	(38)		x	x	x	x	x
Symptom preoccupation scale (SYMPs)	Symptom preoccupation	Not yet published		x	x	x	x	x
Godin-Shephard Leisure-Time Physical Activity Questionnaire (GSLTPAQ)	Physical activity	(39)		x	x	x	x	x
Adapted self-efficacy scale	Self-efficacy	(40)		x	x	x	x	x
Credibility/Expectancy scale (C/E scale)	Credibility and expectancy	(21)			w. 2			
Working Alliance Inventory (WAI)	Relationship with the therapist	(41)			w. 2			
Explicit evaluation of therapy								
8-item Client satisfaction questionnaire (CSQ-8)	Satisfaction with treatment	(22)				x		
20-item Negative Effects Questionnaire (NEQ-20)	Negative effects of treatment	(23)				x		
Cost-effectiveness outcomes								
EuroQol 5D (EQ5D)	Utility score	(42)		x		x	x	x
Trimbos questionnaire (TIC-P)	Resource use	(43)		x		x	x	x

SN = screening, PRE = pre-treatment, WK = weekly, PST = post-treatment, 6/12MFU = 6/12-months follow-up

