a) Patients with heightened scores are assessed by a clinician, and referred to routine care services if necessary

b) For the weekly (non-screening) measurements, rephrased to concern the past week.

Treatment conditions

General format of Internet-delivered treatment

Therapist-guided online treatment is delivered over 10 weeks, which is proven format (18) recommended for cancer survivors (20). The patient regularly logs in to the encrypted web platform (“BASS”, as provided via the Karolinska Institutet eHealth core facility). Most of the treatment content is conveyed via an illustrated text divided into modules, equivalent of book chapters. Each modules contains an educational text, homework assignments, and questions for reflection. Participants communicate with their therapist via a system reminiscent of email, and receive a reply within about two weekdays. Homework exercises are tailored to the individual needs of the patient. In total, eight modules are completed at a pace of about one module per week. Participants gain access to new models contingent on progress. Therapists receive continuous supervision from the principal investigator.

Open access publication of treatment content

In order to promote transparency and contribute to the research field as well as clinical practice, the treatment content from this pilot study will be transferred to the public domain and published open access online, tentatively via the Open Science Framework (OSF).

Randomized allocation of treatment components

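### Full trial, if funded: the registry windows stop when treatment starts and resume when it ends, so the 10 treatment weeks fall in neither and care use is not counted from randomisation

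*Combined protocol and SAP*

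**What the plan says.** The section *Secondary outcome: registry data on healthcare consumption* makes the collection conditional: "If funding is secured for this secondary outcome, registry data on health care consumption will also be collected". The data requested are those "pertaining to the 2 years immediately before treatment, and the 2 years immediately following treatment". About the smaller study the section says "This will not be implemented in the pilot study", so the point concerns the full trial alone.

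Under *General format of Internet-delivered treatment*: "Therapist-guided online treatment is delivered over 10 weeks". Under *Randomized allocation of treatment components*: "After completion of the pre-treatment assessment, and separately for each cohort, randomization is achieved using a true random number service". Randomisation therefore precedes treatment; the interval between the two is not stated.

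Table 2 holds one other measure of resource use, the self-reported TIC-P, at pre-treatment, post-treatment, 6 months and 12 months. Its recall period is not given. Under *Statistical analysis*, "Health economic analyses will focus on comparing the most potent treatment configuration" with the null group. That section gives no costing period or start date, and it describes no analysis of the registry data. No section adds registry data for the treatment weeks or starts the count at randomisation.

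**The concern.** One window closes when treatment starts and the other opens when it is over. The weeks between are when participants receive different components, and so when care use may first diverge between conditions. The plan itself expects some contacts then: suicidal ideation is rated weekly (Table 2), raised scores lead to a clinical assessment, and, under *Ethical considerations*, "Participants are referred to routine services if necessary". The same section lists worsening of symptoms among the possible unwanted effects.

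A randomised comparison of care use normally starts at randomisation. Here the first part of randomised time would be absent from the extract, and any wait between randomisation and the start of treatment would be classed as baseline. At stake is the registry outcome and, if registry data were used for it, the hypothesis that the best combination is cost-effective against the null group.

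**Working it through.** The plan gives no figure for this point, so there is none to reproduce. The check is arithmetic on the windows.

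**Inputs.** Treatment: 10 weeks (*General format of Internet-delivered treatment*). Each registry window: 2 years (*Secondary outcome*), or 2 × 365.25 / 7 = 104.36 weeks. Assumed, because the documents do not say: treatment starts at randomisation, and it ends at week 10 for everyone.

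**1. Calendar share.**
- Start of treatment to end of second window: 10 + 104.36 = 114.36 weeks.
- Share in neither window: 10 / 114.36 = 8.7%.
- Share of the first year: 10 / 52.18 = 19%.

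**2. Share of care use missed.** Let r be the rate of use during treatment divided by the later rate. The share missed is w = 10r / (10r + 104.36). The documents give no rates, so r is assumed:
- r = 0.5: 5 / 109.36 = 4.6%
- r = 1: 10 / 114.36 = 8.7%
- r = 2: 20 / 124.36 = 16.1%

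**3. Effect on a comparison between groups.** Let a component change use by a proportion p1 during treatment and p2 afterwards, with w taken in the comparison group.
- Change over the whole period: w·p1 + (1 − w)·p2.
- Change seen in the planned window: p2.
- Discrepancy: w·(p1 − p2).

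If p1 = p2 the discrepancy is zero and the relative comparison is unbiased. The absolute difference in use is still short by the share w. If p1 and p2 differ, each percentage point between them shifts the relative change by 0.046, 0.087 or 0.161 points at r = 0.5, 1 or 2.

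**4. Comparison with the null group.** Controls are offered the full content at the 12-month follow-up (*Partial blinding of study design*). If those 12 months run from the end of treatment (assumed), the period before the offer is 10 + 52.18 = 62.18 weeks, and the gap is 10 / 62.18 = 16% of it.

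**The case against.** The strongest reply is that the sentence describes a data request and does not define an endpoint. The wording for the second window may be loose and mean from the start of treatment, which would close the gap. The outcome is conditional on funding, secondary and confined to a later trial for which amendments are foreseen. The nominal gap is equally long in all eight cells. The TIC-P at post-treatment may capture some of the missing use, while the NEQ-20 and the monitoring of adverse events and mood also address harm during treatment.

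Much of this stands and limits the weight of the point. It does not remove it. The text does not say that the second window opens at the start of treatment, and a request drawn up as worded would have a hole. Equal length does not cancel the loss if use in those weeks differs by component. The TIC-P has no stated recall period and is not registry data.

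Three stronger readings are tempting, and the documents do not support them:

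- *The second window opens at a different time for people who stop early.* The documents define no individual end of treatment. A fixed week 10 fits the text at least as well.
- *A large part of a component's effect is lost.* Assume a 20% change during treatment and 5% later, at equal rates of use: 10 × 0.20 = 2.0 and 104.36 × 0.05 = 5.2, so 2.0 / 7.2 = 28% would go uncounted. With 5% in both periods the same sum is 0.5 / 5.7 = 8.7%. The documents give no effects on use, so nothing favours the first pair.
- *A component that provokes contacts would look neutral or cost-saving.* That needs effects of a particular size and sign, and an analysis resting on the registry alone, which the plan does not specify.

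**Conclusion.** The point holds as a gap in the planned extract. On the plain wording, 10 of about 114.4 weeks (8.7%) are in neither window, care use is not counted from randomisation, and any wait before treatment is counted as baseline. The 8.7% assumes that treatment starts at randomisation and lasts 10 weeks for all.

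The share of care use missed cannot be found from the documents; 4.6% to 16.1% is the range for assumed rate ratios of 0.5 to 2. Neither the direction nor the size of any bias between groups can be stated. It is zero on the relative scale if proportional effects are the same during and after treatment. The consequence is modest, but it is worth settling before any registry request is made, because the repair costs so little.

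**What to change.** Replace the two windows with one continuous extract from 2 years before randomisation to 2 years plus 10 weeks after it. Define the outcome as all care used from the date of randomisation over that same fixed length for everyone, whether or not treatment was completed. Report the 10 treatment weeks as a sub-period.

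For comparisons with the null group, also report the period up to the 12-month follow-up separately. Counting from randomisation does not by itself give a clean contrast with that group, because controls are then offered the full material and the later part of the window may include their use of it.

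The cost is a short protocol amendment, 10 more weeks in the same registry request and a little more analysis. It needs no extra patient contact.
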